**Figure 2. Algorithm to Assess Thromboembolic Events Risk for PE**

Any subject with a total Wells prediction score  $>4$  for PE assessment should have further diagnostic testing per study site standard of care to confirm the occurrence of a TE (Figure 2).

Any subject with a total Wells prediction score  $\leq 4$  for PE assessment and a positive D-dimer value (i.e., above Baseline and out of normal range of the reporting laboratory) should have further diagnostic testing per study site standard of care to confirm the occurrence of a TE (Figure 2).

## Appendix 7      Hemolysis Detection

### Schedule of the Procedures:

Study visit	Blood collection	Urine collection	Clinical parameters	Hemolysis detection assessment
Day 0 (prior IP infusion)	X (within 8 hours prior IP infusion)	X (within 8 hours prior IP infusion)	X	X
Day 1 (post-completion of IP infusion)	X (between 8 and 24 hours post-completion of IP infusion)	X (between 8 and 24 hours post-completion of IP infusion)	X	X
Day 7 ( $\pm$ 1 day)	X	X	X	X
Day 28 ( $\pm$ 2 days)	X	X	X	X

Assessment of hemolysis detection may be performed later, once laboratory results are available, blood and urine collection as well as the evaluation of clinical parameters must be performed as stated in the schedule of procedures.

### Description of the procedures:

For the detection of hemolysis, the following procedure will be carried out to all the study population:

1. Blood testing: whole blood hemoglobin, serum or plasma free hemoglobin, haptoglobin, LDH, DAT, ARC, RBC, hematocrit, TBL and indirect bilirubin, and blood smear.
2. Urine testing: urinary sediment and hemoglobinuria.
3. Clinical parameters including red/dark urine, jaundice, as well as other signs and symptoms of anemia (such as pallor or tachycardia).

### Definition of hemolysis associated with the use of IGIV:

In this clinical trial, an IVIG-associated hemolytic reaction is one in which there is evidence of a new hemolytic process within 7 days of the first IGIV administration [38]. The following laboratory signs must be present:

1. Drop in whole blood hemoglobin of  $\geq 10$  g/L\*

AND

2. Positive DAT

AND

3. At least 2 of:

- increased ARC*	- hemoglobulemia
- increased LDH level*	- hemoglobinuria
- significant spherocytosis	- low haptoglobin level*
- unconjugated hyperbilirubinemia	

\*Changes from the previous blood testing i.e. from Day 0 to Day 1, from Day 1 to Day 7 ( $\pm 1$  day) and from Day 7 ( $\pm 1$  day) to Day 28 ( $\pm 2$  days).

Subjects from this study may be severely ill and may have anemia for a number of reasons. Therefore, it is important to exclude the underlying conditions and concomitant medications as a cause of anemia. The exclusions are:

- History or examination consistent with an alternative cause of anemia including blood loss (e.g. frequent phlebotomy is highly associated with changes in hemoglobin and hematocrit levels for patients admitted to an internal medicine service [39-40]), iron-deficiency anemia, other drug-induced hemolytic anemia, or anemia associated with an underlying disease (e.g. autoimmune hemolytic anemia [41-42]).
- Negative DAT.
- Absence of other inclusion criteria, in particular absence of evidence for hemolysis.

## Appendix 8      Summary of Changes for Amendment 3

(Note: Administrative changes including minor administrative corrections and the changes in the protocol synopsis are not included in Protocol Summary of Changes.)

Sections	Change From: (Strikethrough is added to highlight deleted text):	Change To: (Underline is added to highlight new text)	Rationale:
3.2.2 – Exclusion Criteria	
15. Subjects with a history of chronic alcoholism or illicit drug abuse (addiction) in the 12 months preceding the <del>Screening</del> Visit.
 
19. Subjects currently receiving, or having received within 3 months prior to the <del>Screening</del> Visit, any investigational medicinal product or device.
 
24. Subjects with haemoglobin levels <9<del>mg</del>/dL.
	
15. Subjects with a history of chronic alcoholism or illicit drug abuse (addiction) in the 12 months preceding the Baseline Visit.
 
19. Subjects currently receiving, or having received within 3 months prior to the Baseline Visit, any investigational medicinal product or device.
 
24. Subjects with haemoglobin levels <9g/dL.
	
Clarification provided as there is no Screening Visit in this study.
 
Haemoglobin units corrected.

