### 3.7.3.2 Hemolysis Testing

Laboratory assessments (whole blood hemoglobin, serum or plasma free hemoglobin, haptoglobin, LDH, DAT, ARC, RBC, hematocrit, TBL, indirect bilirubin, and blood smear) will be conducted on Day 0 (prior infusion), Day 1 (after infusion), Day 7 ± 1 and Day 28 ± 2 for hemolysis detection. Note: Local laboratory is to be utilized for testing and reporting. If the local laboratory is unable to perform any of the assessments, the central laboratory may be utilized.

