##### 4.4.7.2 Hemolysis

Subjects will be monitored for signs and symptoms of hemolysis. In addition, the Grifols Medical Monitor will routinely review reported AEs for possible hemolysis. Hemolysis will be recorded as an AE and reported accordingly.

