For summary purpose, AEs will be classified as treatment emergent AEs (TEAEs) or non-TEAEs depending on the comparison of AE onset date/time with the start date/time of study treatment. A TEAE will be defined as an AE which occurs between the beginning of the first infusion of IGIV-C and the final visit of the clinical trial. A non-TEAE will be defined as an AE which occurs prior to the beginning of the first infusion of IGIV-C. Non-TEAEs and TEAEs will be summarized separately.

All AEs will be summarized for subject incidences and percentages by system organ class and preferred term.

In addition, the incidence of TEAEs, including suspected ADRs and ARs, will be summarized by system organ class, preferred term, causal-relationship, intensity (severity) and seriousness (serious vs. non-serious) using descriptive statistics. At each level of summarization, a subject will only be counted once per system organ class or preferred term using the most severe or causal relationship AE.

AEs temporally associated to the infusion of the IP (i.e., infusional AEs, including infusional suspected ADRs), will be separately summarized. AEs occurring during the two-day infusion period (i.e., from the initiation of the IP infusion on the first day to the completion of the total dose of IP on the last day) and within 72 hours following the completion of the infusion of the total dose of IP on the last day, regardless of other factors that may impact a possible causal association with product administration, will be defined as infusional AEs (i.e., an AE temporally associated with an infusion of the IP). In addition, the infusion rate in effect at the time of onset of the AE, the time the AE is first reported and the time the AE changes materially in intensity and/or resolves will be also reported and listed.

Subjects with deaths, SAEs, and AEs leading to premature discontinuation from the study will be listed and presented in a narrative form. Subjects with TEAEs of special interest (thromboembolic events and hemolytic event) will be listed separately. The Wells score will be listed.

Vital signs

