Vital signs (T, RR, HR, SBP and DBP) will be descriptively summarized and listed for each subject. Summaries will be presented for the original value and change from Baseline. Abnormal vital signs judged as clinically relevant by the Investigator will be considered AEs. In case a subject presents a clinically relevant abnormality of vital signs during an infusion, the event will be flagged and reported as an AE temporally associated to the infusion. For each subject and for each infusion, every vital sign will be considered. Clinical relevance will be based on the Investigator's criteria.

Physical Assessment

Physical Exam findings on Day 0 (normal and abnormal) and any change at final visit/early termination will be listed for each subject. Abnormal findings judged as clinically relevant by the Investigator will be considered AEs. A summary table will also be provided by visit.

Blood biochemistry and hematology

All clinical laboratory data for renal, hepatic and hematological parameters will be listed for each subject. Laboratory results out of the normal range will be presented in shift tables. Laboratory results out of the normal range judged by the Investigator as clinically relevant will be considered AEs.

Lab test for thromboembolic events and hemolysis

The D-dimer for thromboembolic assessment and the laboratory tests for detecting hemolysis will be tested at local labs and listed, and out of normal range results will be flagged.

A listing of laboratory tests used for applicability of the algorithm for hemolysis event determination from Baseline to the end of study will be provided that includes all direct antiglobulin test (DAT) results, and all hemoglobin, absolute reticulocyte count, serum/plasma free hemoglobin, haptoglobin, LDH, and total direct and indirect bilirubin values at corresponding time points. Blood smear results (specifically whether there is presence of spherocytosis) and hemoglobinuria on urinalysis will also be included.

12 Interim Analysis

No interim analysis is planned.

13 Changes in Planned Analysis

A shift table will be provided for AChR antibodies (or MuSK antibodies) from Baseline (Day 0) to Day 14 and Day 28.

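### The required haemoglobin drop counts only from the previous sample, so equal Day 0 to Day 7 falls can be classified differently and no SAP listing marks this; the 7-day limit and the Day 7 to Day 28 comparison need reconciling

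*Protocol*

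**What the plan says.** Protocol Appendix 7 states that "an IVIG-associated hemolytic reaction is one in which there is evidence of a new hemolytic process within 7 days of the first IGIV administration". Three laboratory conditions are joined by AND: "Drop in whole blood hemoglobin of" 10 g/L or more, a positive DAT, and at least two of seven further signs. An asterisk on the haemoglobin, ARC, LDH and haptoglobin items leads to the footnote "Changes from the previous blood testing i.e. from Day 0 to Day 1, from Day 1 to Day 7" (± 1 day), and finally from Day 7 to Day 28 (± 2 days). Exclusions for other causes of anaemia follow. On phlebotomy the appendix notes that "frequent phlebotomy is highly associated with changes in hemoglobin and hematocrit levels for patients admitted to an internal medicine service".

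Protocol 3.7.3.2 schedules the blood tests at Day 0, Day 1, "Day 7 ± 1 and Day 28 ± 2 for hemolysis detection". Protocol 4.4.7.2 adds medical monitor review of reported AEs and says "Hemolysis will be recorded as an AE and reported accordingly".

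SAP Section 11 has three relevant provisions:

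- A general statement that "the laboratory tests for detecting hemolysis will be tested at local labs and listed, and out of normal range results will be flagged".
- A separate listing, from Baseline to end of study, of the tests that feed the hemolysis algorithm, including haemoglobin and DAT. No change column or flag is specified for it.
- For events, "Subjects with TEAEs of special interest (thromboembolic events and hemolytic event) will be listed separately".

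**The concern.** The footnote's list of pairs is closed, and neither document adds a Day 0 comparison at Day 7. Because all three conditions are required, a positive DAT and further signs cannot rescue a subject whose fall is spread over both intervals. Two subjects with the same total fall by Day 7 can then be classified differently only because of the Day 1 value. Hemolysis is one of two adverse events of special interest, so its classification should not turn on that.

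The definition also sets a limit of seven days from the first infusion, yet its own footnote prescribes a comparison ending at Day 28. Two reviewers could classify a drop first seen at Day 28 differently.

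**Working it through.** The plan states no figure to reproduce here, so the check applies the rule itself.

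**The rule.** Let *a* be the fall from Day 0 to Day 1, *b* the fall from Day 1 to Day 7, and T = a + b. As written, the criterion is met by Day 7 if a ≥ 10 or b ≥ 10 g/L. It fails when both are below 10, that is when T − 10 < a < 10. Such splits exist for every T below 20 and for none at T ≥ 20. The exposed range is therefore 10 ≤ T < 20 g/L.

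| Day 0 / 1 / 7 (g/L) | a | b | T | Criterion as written |
|---|---|---|---|---|
| 120 / 115 / 106 | 5 | 9 | 14 | fails |
| 120 / 118 / 106 | 2 | 12 | 14 | met |
| 120 / 126 / 115 | −6 | 11 | 5 | met |

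The third row shows that the previous-sample comparison also catches cases that a Day 0 comparison alone would lose.

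**Whole-number splits.** With a = 0, …, T, the failing splits number 19 − T out of T + 1: 9 of 11 at T = 10, 7 of 13 at 12, 4 of 16 at 15, 1 of 19 at 18, and none at 19. These are counts of possibilities, not probabilities.

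**Steady decline, no measurement error.** Assume a linear fall from the start of the first infusion, and a second infusion that starts at 24 h and lasts 2–8 h. The Day 1 sample, 8–24 h after its end (Appendix 7), then falls at 34–56 h. Day 7 ± 1 is 144–192 h. The share of the fall lying between Day 1 and Day 7 runs from (144 − 56)/144 = 0.61 to (192 − 34)/192 = 0.82. Falls from 10 up to 10/0.82 = 12.2 g/L, or up to 10/0.61 = 16.4 g/L, fail.

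**With measurement error.** Add independent normal error to each sample. The documents give no SD; 2 and 4 g/L are assumed. The table gives the simulated share meeting the haemoglobin criterion.

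| True fall by Day 7 | SD | As written | With Day 0 comparison added |
|---|---|---|---|
| 12 g/L | 2 | 20–49% | 77–81% |
| 15 g/L | 2 | 45–80% | 96–98% |
| 12 g/L | 4 | 48–56% | 71–74% |
| 15 g/L | 4 | 63–73% | 85–88% |

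**Cost on the same model.** Suppose all 50 planned subjects drift down 8 g/L for non-hemolytic reasons.

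- SD 2: 0.043–0.115 as written, so 50 × 0.043 = 2.2 to 50 × 0.115 = 5.8. With Day 0 added, 0.253–0.290, so 12.7 to 14.5.
- As a hand check at SD 2, the SD of a difference is 2√2 = 2.83. At share 0.82, b = 6.6 and a = 1.4, and P(Z ≥ 1.21) + P(Z ≥ 3.03) ≈ 0.113 + 0.001, or about 0.115.
- SD 4: 0.292–0.335 as written, so 14.6 to 16.8. With Day 0 added, 0.456–0.484, so 22.8 to 24.2.
- No drift at all: about 0 extra at SD 2 and about 1 extra at SD 4 (50 × 0.077 = 3.9 against 50 × 0.099 = 4.9).

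**Timing.** The first sample of the last pair falls on Day 6, 7 or 8 and the second on Day 26 to 30, so the interval is 18 (26 − 8) to 24 (30 − 6) days long. At most one day of it, when the first sample is on Day 6, lies inside the 7-day limit. The later sample is 26 − 7 = 19 to 30 − 7 = 23 days past the limit.

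**The case against.** The strongest case is that an interval-by-interval rule is a legitimate choice. Appendix 7 attributes the definition to a cited source that cannot be checked here. These patients may become anaemic for many reasons, and a week-long comparison with Day 0 picks up more of that drift than a shorter interval. This stands: adding Day 0 as a qualifying comparator would buy sensitivity with specificity, as the drift figures show. It is a reason not to rewrite the definition, but it does not make the classification of equal falls consistent.

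It can also be said that nothing is hidden. The algorithm listing puts Day 0 and Day 7 haemoglobin side by side for about 50 subjects, the medical monitor reviews reported AEs for possible hemolysis, and investigators can report it on judgement. This stands in part. The values are visible, but no step computes or marks the cumulative fall. The route by which laboratory results become AEs (Protocol 4.3.4) concerns out-of-range results. The shift tables cover the biochemistry and hematology panels, which are scheduled only at Day 0 and Day 28.

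A reader might infer that the only flag on the algorithm listing is for out-of-range values. The SAP states that flag for the general hemolysis listing and is silent on flags for the algorithm listing.

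On timing, the footnote may simply mirror the sampling schedule, with the 7-day sentence limiting what counts. On that reading the last comparison cannot by itself establish a qualifying reaction, and the text should say so.

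**Conclusion.** The point holds as a minor weakness of the classification rule. A Day 0 to Day 7 fall of 10 to just under 20 g/L can meet or fail the mandatory haemoglobin criterion according only to its split around Day 1, and the SAP plans nothing that marks the pattern. That range follows from the rule alone and needs no assumption. The percentages and drift counts rest on an assumed linear decline, infusion length and error SD.

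A reader might take the split counts or percentages as rates of missed hemolysis, or conclude that the Appendix 7 definition is wrong and must be replaced. The documents support neither. DAT, two further signs and the exclusions apply as well, nothing shows how often falls are split, and the previous-sample rule contradicts no other section. The effect is further limited because investigator reporting and medical monitor review may still capture these cases.

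The 7-day limit and the Day 7 to Day 28 comparison do conflict within one definition. A drop first seen at Day 26–30 cannot be dated to the first seven days. A sample taken on Day 8 is a lesser problem, since it can reveal a process that began by Day 7.

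**What to change.** 1. Keep the Appendix 7 definition as the main classification.
2. In the SAP's algorithm listing, add a column for haemoglobin change from Day 0 and a flag for subjects whose drop is at least 10 g/L from Day 0 but not from the previous sample.
3. Report, as a supportive classification, the flagged subjects who also have a positive DAT, have at least two further signs and are not removed by the exclusions. Leave the ARC, LDH and haptoglobin comparisons as written.
4. Reconcile the 7-day limit with the Day 7 to Day 28 comparison in Appendix 7. This review does not say which time limit is right. Whichever is kept, apply the Day 0 column and flag to every sample within it.

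The cost is one column, one flag, a short supportive table and a clarifying sentence in Appendix 7. The samples are already scheduled. There will be more candidates to review: in the drift scenario, about 13–15 subjects instead of 2–6 (SD 2 g/L), or 23–24 instead of 15–17 (SD 4 g/L), would meet the haemoglobin criterion on one comparison or the other. These counts are before DAT, the further signs and the exclusions reduce them. The main classification does not change, so the specificity loss is confined to the supportive one.

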### 1.2 Management of MG Exacerbations

Management for myasthenic exacerbations should be carried out in an intensive care unit (ICU) or general ward staffed with physicians who are experienced in the management of MG, respiratory insufficiency, infectious disease, and fluid and electrolyte therapy (1,10). After stabilizing the patient and securing the airway, respiration, and haemodynamics, options for specific treatment include use of acetylcholinesterase inhibitors, plasma exchange (PLEX), intravenous immunoglobulin (IGIV), and immunosuppressive drugs (such as CS), (11). Autoantibody activity in MG can be modulated by either removal from plasma by PLEX or selective immunoabsorption techniques or by the expansion of the immunoglobulin

pool by administering high-dose IGIV that interferes with the autoantibody activity by means of several and still poorly understood pathways (12). CS administration results in a gradual effect on symptoms, which starts after a few days and is clinically obvious after approximately 2 weeks, but maximum benefit may take months (13,14). Initial treatment with prednisone may lead to an exacerbation of MG in almost half of the patients attempted and it is recommended that initiation of CS should occur in a hospital setting where respiratory function can be monitored (15). Additionally, if patients experience an MG exacerbation and are already receiving CS, then CS use should not be discontinued while treating the exacerbation (15).

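### The first hemolysis exclusion in Protocol Appendix 7 can rule out a case that meets every laboratory criterion, and no count before and after exclusions is planned

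*Protocol*

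**What the plan says.** Protocol Appendix 7 states that "an IVIG-associated hemolytic reaction is one in which there is evidence of a new hemolytic process within 7 days" of the first administration. It continues: "The following laboratory signs must be present". Three criteria follow, joined by AND:

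1. a fall in whole blood haemoglobin of at least 10 g/L;
2. a positive DAT;
3. at least two of seven markers: raised absolute reticulocyte count, raised LDH, spherocytosis, unconjugated hyperbilirubinemia, free haemoglobin in blood, haemoglobin in urine, low haptoglobin.

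The appendix then explains why exclusions are needed: "Subjects from this study may be severely ill and may have anemia for a number of reasons", and "Therefore, it is important to exclude the underlying conditions and concomitant medications as a cause of anemia". Three exclusions are listed. The first begins "History or examination consistent with an alternative cause of anemia including blood loss (e.g. frequent phlebotomy" and goes on to name iron-deficiency anemia, other drug-induced hemolytic anemia, and anemia from an underlying disease such as autoimmune hemolytic anemia. The second is a negative DAT. The third is absence of the other criteria.

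Protocol 4.3.6 refers to Appendix 7 for detection and says that hemolysis is recorded as an AE. Protocol 4.4.7.2 makes it an event of special interest. SAP Section 11 says "Subjects with TEAEs of special interest (thromboembolic events and hemolytic event) will be listed separately" and also promises a listing of the laboratory tests that feed the hemolysis algorithm, from Baseline to the end of the study.

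**The concern.** The first exclusion requires only that the history or examination be compatible with another cause of anemia. The laboratory definition asks for much more than anemia: it requires immune evidence (the DAT) and evidence of red-cell destruction (the markers). An explanation for one part of the definition can therefore cancel a case that satisfies all of it.

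Hemolysis is one of two events of special interest. The study is open-label with no control arm (Protocol 3.1), so no comparison group would show that cases were being under-classified. A low reported number of hemolytic reactions could then reflect the product, the exclusion, or both, and the planned summaries would not separate them.

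**Working it through.** The documents give no hemolysis rate, phlebotomy rate or exclusion rate, so there is no planned figure to reproduce. The check is a reading of the text, followed by an illustration on stated assumptions.

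**Which exclusion can change a classification.** Take a case that meets criteria 1 to 3. The negative-DAT exclusion cannot apply, because criterion 2 requires a positive DAT. The exclusion for absence of the other criteria cannot apply either. Only the first bullet can remove such a case.

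**What the first bullet asks for.** It gives no number of draws, blood volume or haemoglobin level. It names nobody to decide. It does not say which of the laboratory findings the other cause must explain.

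**What the named causes could explain.** This step is general haematology, not a statement in the documents. Autoimmune or other drug-induced hemolytic anemia could account for the DAT and the markers, so excluding on those grounds is coherent. Blood loss could account for the haemoglobin drop and for one of the seven markers, a raised reticulocyte count. Criterion 3 needs at least two markers, so at least one other marker and the positive DAT remain unexplained. Iron deficiency raises the same question. The bullet treats both kinds of cause alike.

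**What remains visible.** The SAP Section 11 listing covers haemoglobin (criterion 1), all DAT results (criterion 2), and reticulocytes, LDH, bilirubin, free haemoglobin, haptoglobin, spherocytosis and hemoglobinuria (all seven markers of criterion 3). No exclusion filter is stated. A reader could rebuild the number meeting criteria 1 to 3 by hand. Neither document plans to report that number, or who was excluded and for what reason.

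**Direction.** Exclusions remove cases and never add them, so the number classified cannot exceed the number meeting criteria 1 to 3.

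**Illustration.** Inputs: N = 50 planned subjects (Protocol 5.2); p, the assumed true rate of cases meeting criteria 1 to 3; f, the assumed share of those cases ruled out. Neither p nor f is in the documents.

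P(at least one classified case) = 1 − [1 − p(1 − f)]^50; expected number = 50 × p × (1 − f).

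Example with p = 0.05 and f = 0.5: 1 − 0.975^50 = 0.718; expected 50 × 0.05 × 0.5 = 1.25.

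| p | f = 0 | f = 0.5 | f = 0.9 |
|---|---|---|---|
| 0.02 | 0.636 (1.0 expected) | 0.395 (0.5) | 0.095 (0.1) |
| 0.05 | 0.923 (2.5) | 0.718 (1.25) | 0.222 (0.25) |
| 0.10 | 0.995 (5.0) | 0.923 (2.5) | 0.395 (0.5) |

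The result depends heavily on f, for which the documents offer no value.

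**The case against.** The strongest reply is that the clause calls for a causal judgement on each case and does not operate automatically. The sentence before the list gives its purpose as excluding other conditions as a cause of anemia, and a sensible assessor would not discard a DAT-positive case because blood had been drawn. That is a fair reading of the intent. It does not repair the wording, which sets the bullet beside a negative DAT as an exclusion of equal standing.

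A second reply is that little is hidden. The laboratory inputs are all listed. AE recording under Protocol 4.4.7.2 and the listing of hemolytic TEAEs in SAP Section 11 are not expressly limited to cases that survive the exclusions, and the sponsor's medical monitor reviews reported AEs for possible hemolysis. This stands. The documents do not say that an excluded case goes unrecorded. Even so, Protocol 4.3.6 points to Appendix 7 for detection and no other definition is given, so an excluded case may well not be classified as hemolysis.

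A third reply is that the definition cites a published source and may follow it. That cannot be checked from these documents. Reporting counts before and after exclusions would keep any comparability with that source.

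A reader might go further and infer that the clause removes most subjects, since Protocol 1.2 says "Management for myasthenic exacerbations should be carried out in an intensive care unit (ICU) or general ward" and the protocol itself draws blood at four scheduled time points up to Day 7. The documents do not support this. The setting statement is background, no draw volumes are given, and four draws are nowhere called frequent. The only phlebotomy evidence offered is that "frequent phlebotomy is highly associated with changes in hemoglobin and hematocrit levels for patients admitted to an internal medicine service", which is an association and not a rate in this population.

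**Conclusion.** The point holds as a gap in wording and reporting. As written, Appendix 7 permits a case meeting criteria 1 to 3 to be classified as not IGIV-associated hemolysis because of a history compatible with blood loss or iron deficiency, without asking whether that history explains the DAT and the markers. Its effect on the count can only be downward; its size is unknown. If p were 5%, the chance that 50 subjects yield at least one classified case would run from 0.923 with nothing ruled out to 0.222 with 90% ruled out, but both inputs are assumptions.

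It would be wrong to conclude that most true cases would be lost, that the sickest subjects would be removed selectively, or that excluded cases disappear from the report. No figure in the documents supports the first two, and the laboratory listing contradicts the third. This is a cheap improvement and not a flaw that undermines the safety analysis.

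**What to change.** **SAP Section 11:** add one table with the number and percentage of subjects in the Safety population who meet Appendix 7 criteria 1 to 3, the number remaining after exclusions, and the reason for each exclusion. The first count uses laboratory data already collected and listed.

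**Protocol Appendix 7:** state that blood loss or iron deficiency excludes a case only if it accounts for the hemolysis findings (positive DAT and markers), and not if it accounts for the haemoglobin drop alone. The hemolytic causes in the same bullet can stay as they are. This changes how events are classified and does not affect patient care.

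**Cost:** wording changes in two documents, one extra table, and documentation of a reason whenever a case is excluded. The count before exclusions may look less favourable than the count after. If the appendix is not amended, the SAP table is still worth adding, because it lets readers see how much the exclusions matter.
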